### **Phase II**

**2. To assess preliminary outcomes of the ESTIMA HIV Prevention Program** Using a two-armed randomized controlled design, we will recruit FSW (n=120, 60 in each arm) who will be randomized to: 1) the ESTIMA intervention (gender equity program and *Via* microfinance program) or 2) a wait-list control group. Women will be part of groups of approximately 10 women each, and each group will be randomized to intervention or control conditions. At 12 months follow-up, we hypothesize that compared to control participants, intervention participants will have: **a)** Significantly greater economic security (e.g. decreased debt, increased income, decreased number of sex trades) and **b)** Significantly greater perceived collective power (i.e. collective efficacy) to address gendered power imbalances within social structures and the community.

**3. To assess feasibility regarding all aspects of implementation, receptivity by participants and staff, and capacity to be maintained by *Via* microfinance efforts** Qualitative focus groups (n=2 or less per intervention group, 10 women per session), individual interviews (approximately 5 per intervention group), and quantitative assessments will be conducted with intervention participants, along with staff feedback via post-training evaluation forms, to inquire about satisfaction with and appropriateness of the program, as well as aspects pertinent to the ethical conduct of the intervention. We will also monitor recruitment, random assignment, adherence to intervention design, retention of participants, contamination across arms, and the incidence of adverse events.

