## **Phase II**

### **Specific Aim 2: To assess preliminary outcomes of ESTIMA**

**Recruitment and Random Assignment.** We will recruit ESTIMA participants from those who are completing 12 month follow-up for the parent study, using the same eligibility criteria and recruitment in Specific Aim 1 (assessing interest among those who indicate willingness to be recruited into a sub-study and based on responses in their surveys from the parent study), with an additional criteria related to women's drug use frequency; the specific criteria will be determined based on Aim 1 findings, consultation from the CAB and *Via* microfinance (drug use data will be retrieved from the parent survey; 41% and 53% of participants from the parent study report using drugs and alcohol less than once per week respectively). *Those who participated in Aim 1 and who fall within these eligibility criteria will be eligible for participation.* Research staff of the K01 and parent grant will work jointly to identify those willing and eligible during the 12 months follow-up data collection of the parent grant. From the parent study, we will recruit a total of 120 participants in expectation to afford a final sample size of at least 48 in each group (using a conservative estimate of 80% retention). Eligible and willing participants will be randomized to treatment assignment (ESTIMA or wait-list control group) using a randomizer software package, after enrollment. The microfinance groups of women (approximately 6-10 per group) will be formed and randomized to intervention or wait-list control condition. The wait-list control group will be provided with referrals to local FSW support organizations, as the standard of care (STI/HIV testing and referrals), and will receive ESTIMA subsequent to the 12 month follow-up data collection. ESTIMA will involve groups of approximately 6-10 women each; groups will initiate once sufficient numbers are enrolled (i.e. groups will be staggered in terms in initiation).

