
Outcome Measures. Measures on GBV, gender, HIV, and health were drawn from Demographic Health Surveys (DHS), multiple instruments previously used by investigators, as well as items from the IMAGE study adapted for use in this Mexican context. New items will be added to parent grant surveys (e.g. collective efficacy, additional economic stability variables, women's status indicators) based on Aim 1 findings. Measures will include relevant demographic variables (e.g. age, education, living situation and evictions, other employment, head of household, economic support, number of children). We will include assessments on collective efficacy/power (e.g. perceptions of power in addressing GBV and gender inequity collectively) and women's economic stability using several variables (assessing debts, income, number of sex trades and income from sex trades, other income generating efforts, income independence, economic mobility, self-efficacy and confidence in maintaining financial security, variables measuring consumption-including monies spent on children's needs and education). We will also measure knowledge of gender inequity issues, HIV, and interactions between GBV and HIV, gender equitable attitudes, attitudes around GBV (7 items assessing justification of violence against women), and women's status indicators (including women's economic and social decision-making in household, women's economic mobility, e.g. gender-based challenges in engaging in business or managing finances). GBV will be measured as physical, sexual and psychological acts of violence perpetrated by clients, male partners, and other men in the community, using an internationally adapted Conflict Tactics Scale. Frequency of unprotected sex will be constructed from items assessing the number of times participants had vaginal or anal sex with clients and male partners in the past 90 days and the number of times they used a condom during sex. Measures on alcohol use in the supplemental survey were drawn from recommendations from the World Health Organization and the National Institute on Alcohol Abuse and Alcoholism. Measures on discrimination were adapted from a variety of scales frequently used in social psychology, including the Perceived Discrimination scale and Schedule of Sexist Events scale.

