sexual health risk indicators). The distributional properties and reliability of continuously scaled variables will be examined. Effects of the intervention on both intermediate and long-term outcomes (see Figure 1) will be examined using logistic regression analyses for dichotomous variables (e.g. GBV, consistent condom use) and ANCOVA for continuous variables (e.g. collective efficacy scales, income, number of sex trades). Analyses will focus on outcomes at the 12 month follow-up. ANCOVA using ranks will be used to examine outcome variables with non-normal distributions, such as income. While ESTIMA is powered to focus on intermediate outcomes, we will also investigate trends on longer term outcomes as well (Figure 1). We expect low rates of loss to follow-up, as ESTIMA is incorporated into existing *Via* trainings; however, we will track any participants who drop out of the program (Aim 3), as well as loss to follow up. If there is more than a trivial amount of missing data, we will examine whether there are any patterns in missing data by relevant study variables (e.g. violence experiences, demographic characteristics etc). Power calculations were performed using a significance level of 0.05 and 80% retention (n=48 in each group), with focus on **primary intermediate outcome variables** (economic security and collective power variables) (Figure 1). For analysis focused on variables of income and debt, number of sex trades, as well as the scales measuring women's collective power, we will have 80% power to detect a standardized effect size of 0.5, which is considered a moderate effect size based on work from Cohen (1988). We believe that a moderate effect size would be needed in order to ensure that the effect of the intervention is significant for wide-scale adoption and sufficient impact. However, because we will have small numbers for this pilot of the ESTIMA project, we recognize that we may only be able to find trends to report, and which will be used to secure further funds to run a full-scale trial. While we have not powered the trial to detect a significant effect on GBV, HIV risk behaviors, or HIV/STI, we anticipate a trend toward decreased reports of these in the intervention group compared to the control arm. Furthermore, collecting information on GBV, HIV risk, and HIV/STI will also provide information to power a subsequent larger-scale evaluation.

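### The economic-security hypothesis rests on at least three primary variables at a single 0.05 level, with no adjustment and no rule for which variable decides

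*Combined protocol and SAP*

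**What the plan says.** Sections 5 and 6 state two hypotheses at 12 months, both worded as significant differences. Hypothesis (a) reads "Significantly greater economic security (e.g. decreased debt, increased income, decreased number of sex trades" and so on: an open list of examples. Hypothesis (b) concerns perceived collective power, which the text equates with collective efficacy.

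Section 9, Quantitative Data Analyses and Power Calculations, calls the economic security and collective power variables the primary intermediate outcomes. It then says: "Power calculations were performed using a significance level of 0.05 and 80% retention (n=48 in each group". The variables covered are given as "For analysis focused on variables of income and debt, number of sex trades, as well as the scales measuring" women's collective power, and for these "we will have 80% power to detect a standardized effect size of 0.5". Continuous outcomes are analysed by ANCOVA, on ranks where non-normal, with the focus on 12 months.

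Section 9, Outcome Measures, lists economic stability more widely, "using several variables (assessing debts, income, number of sex trades and income from sex trades, other income generating efforts" and further items. It adds that new economic and collective-efficacy items may follow from the Aim 1 findings.

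The supplied text contains no multiplicity adjustment, composite, hierarchy, or statement of which variable, or how many, must be significant for a hypothesis to be met. Section 9 refers to Figure 1 for the outcome framework. That figure is not shown in the copy reviewed.

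**The concern.** A claim of significance for economic security needs a known error rate. With three or more variables able to carry the claim and nothing said about which one does, the error rate is not the 0.05 in the power statement, and the deciding variable could be settled after the results are known.

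The variables can also disagree. Sections 14 and 15 acknowledge that some women may take on more clients to repay the loan. Income could then rise because sex trades rise, so that one variable supports hypothesis (a) while another contradicts it. The plan does not say what would be concluded. A multiplicity correction alone would not settle that, whereas a named deciding variable would.

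The results are meant to help obtain funding for a full-scale trial, so a finding picked from several variables would carry over into that decision.

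**Working it through.** **Inputs from the documents.** Significance level 0.05; standardized effect 0.5; 80% power; 48 analysed per arm (Section 9). Enrolment is 60 per arm (Section 6: "we will recruit FSW (n=120, 60 in each arm"). Retention is 80%, and 48 / 0.80 = 60, so the enrolment figure agrees.

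**Inputs assumed.** Sidedness is not stated. The correlation between outcomes is not given, so 0 to 0.7 is used. The 0.05 stated for the power calculation is taken as the level for each test.

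**Step 1: the plan's own power figure.** For two means, power = Φ(d·√(n/2) − z), with d·√(n/2) = 0.5 × √24 = 2.449.
- Two-sided 0.05: Φ(2.449 − 1.960) = Φ(0.489) = 68.8%.
- One-sided 0.05: Φ(2.449 − 1.645) = Φ(0.804), about 79%.
- Two-sided ANCOVA with baseline correlation 0.486: 2.449 / √(1 − 0.486²) = 2.803, and Φ(2.803 − 1.960) = 80.0%.

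The stated 80% is therefore met, within rounding, by a one-sided test or by a two-sided ANCOVA with a baseline correlation near 0.49. Both routes use the full 0.05 for one variable, so nothing was set aside for several variables.

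**Step 2: chance of at least one false significant result when there is no effect.** For k independent tests at 0.05 this is 1 − 0.95^k. For correlated tests it was simulated with equally correlated normal test statistics (at least 1,000,000 draws).

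| Variables tested | k | Independent | Correlation 0.3 | 0.5 | 0.7 |
|---|---|---|---|---|---|
| Income, debt, number of sex trades | 3 | 14.3% | 13.6% | 12.6% | 10.9% |
| The same plus one collective-power scale | 4 | 18.5% | 17.4% | 15.6% | 13.1% |
| All economic measures in Outcome Measures plus collective efficacy (assumed) | 10 | 40.1% | 35.2% | 28.8% | 21.3% |

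For the first row, 1 − 0.95³ = 1 − 0.857 = 14.3%. The last row counts nine economic items (debts, income, number of sex trades, income from sex trades, other income generation, income independence, economic mobility, financial self-efficacy, consumption) plus one collective-efficacy measure.

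**Step 3: favourable direction only.** A two-sided 0.05 test puts 0.025 in the favourable tail. For three independent variables the chance is 1 − 0.975³ = 7.3%, and 5.5% at correlation 0.7. That is about half the two-sided figure and compares with 2.5% for one variable. If the tests are meant to be one-sided at 0.05, the favourable-only figure is 1 − 0.95³ = 14.3% if independent and 10.3% at correlation 0.7, against 5% for one variable.

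**Step 4: hypothesis (b).** With a single collective-efficacy score there is one test at 0.05. With two scales the chance is 1 − 0.95² = 9.75% if independent and 8.3% at correlation 0.7. The number of scales is not given.

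**The case against.** The best defence is that this is a pilot. Section 9 says the study may only find trends, to support an application for a full-scale trial. That lowers the stakes. But the caveat is about small numbers, hence missed effects, not false positives, and Sections 5 and 6 still promise significance.

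A second defence is that Figure 1 may define the primary outcomes more closely. It may indeed narrow the list. A conceptual framework is unlikely to contain a testing rule, and none appears in the text.

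A third is that (a) and (b) are stated as separate hypotheses, so no correction across the two is required. That stands, and the fix respects it.

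Three stronger readings are tempting but not supported:
- A reader might infer that a false significant result is likely. It is not: 11-14% on the three named economic variables is well above 5% but far from an even chance. Independent tests pass 50% only at 14 variables (1 − 0.95^14 = 51.2%).
- A reader might take 40% as the plan's error rate. That treats every item in Outcome Measures as a primary test. The section is a general measures list and does not call those items primary.
- A reader might conclude that the plan lets any one favourable variable confirm the hypothesis. The plan does not say so. It is silent on the rule, and that silence is the defect.

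**Conclusion.** The point holds for hypothesis (a). At least three variables are treated as primary under a single 0.05, and the supplied text gives no adjustment or deciding rule. The chance of at least one false significant result is about 11-14%, two to three times the nominal 5%, and about half that in the favourable direction only. Adding one collective-power scale gives 13-19%. If about ten measures were tested, which is an assumption, it would be 21-40%.

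The point applies more weakly to hypothesis (b), which is one construct. Any multiplicity there comes from the plural reference to scales that are neither named nor counted, so it would be wrong to say that both hypotheses are equally open.

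These figures rest on two-sided tests at 0.05 for each variable (inferred), assumed correlations of 0 to 0.7, and each test truly holding its 0.05. The last is a separate matter, because groups are randomized and the analysis paragraph describes no allowance for clustering. Given the pilot purpose this is a should-fix.

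**What to change.** In Section 6 (Phase II) and in the power paragraph of Section 9, and to match in Section 5, before any 12-month data are seen:

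1. Name one deciding economic variable for hypothesis (a) and one collective-efficacy score for hypothesis (b). The choice is the sponsor's.
2. State that each hypothesis is read separately at 0.05, and state the sidedness.
3. Report all other economic and collective-power variables as estimates with 95% CIs and no claim of significance.

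If the sponsor prefers estimation only, removing the significance wording from Sections 5 and 6 would also resolve the point.

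**Cost.** This is a text edit and needs no extra participants. Each named test keeps the power it has now. The price is that the other economic variables can no longer support a significance claim.

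Holm across the two hypotheses is optional. Its stricter first step is 0.025, where two-sided power without a covariate is Φ(2.449 − 2.241) = 58.2%, against 68.8% at 0.05. By comparison, keeping all three economic variables with a Bonferroni level of 0.05/3 would leave 52.2% power for each, so naming one variable costs less.

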**5. LAY LANGUAGE SUMMARY OR SYNOPSIS (no more than one paragraph)**

Given the increasing recognition of the contribution of structural-level factors (e.g. gendered economic and social power imbalances) on both HIV and gender-based violence (GBV) among women, and thereby, the need for interventions that aim to alter such structures within communities, we have developed the proposed research to address the *intersection of GBV and HIV*. The proposed research aims to pilot a multi-strategy structural intervention combining community mobilization to promote gender equity alongside an economic intervention (microfinance and business training) in order to reduce gender-based violence and HIV risk among female sex workers (FSW) in Tijuana, Mexico. The program will be called ESTIMA: “Economic and Social empowerment To Increase upwards Mobility Among women”. The evaluation will employ a randomized controlled design, recruiting FSW (n=120, 60 in each arm) who will be randomized to: 1) ESTIMA (gender equity/community mobilization program and economic intervention) or 2) a wait-list control group. Women will be part of groups of approximately 6-10 women each, and each group will be randomized to intervention or control conditions. For this preliminary work, at 12 months follow-up, we hypothesize that compared to control participants, intervention participants will have: 1) significantly greater economic security (e.g. decreased debt, increased income, decreased number of sex trades) and 2) significantly greater perceived collective power (i.e. collective efficacy) to address gendered power imbalances within social structures and the community. The long-term goal of this program, upon future refinement and large scale implementation, is to reduce HIV risk behaviors, STI/HIV, GBV, and ultimately, alleviate a multitude of health burdens among women. Furthermore, we expect that such work will highlight the need for HIV prevention initiatives in Mexico, and elsewhere, to more broadly consider women’s ‘life contexts’ – addressing economic and social burdens in women’s lives, to reduce the burden of poverty, gender, and HIV, as well as the intersection of these among women.

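### The 80% power for 0.5 SD treats 48 women per arm as independent, and no group term is stated for the analysis, although women are randomised or at least treated in groups

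*Combined protocol and SAP*

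**What the plan says.** The power statement is in section 9, Specific Aim 2, under Quantitative Data Analyses and Power Calculations: "Power calculations were performed using a significance level of 0.05 and 80% retention (n=48 in each group". From these inputs, for income and debt, number of sex trades and the collective-power scales, "we will have 80% power to detect a standardized effect size of 0.5". The planned methods are logistic regression for dichotomous outcomes and "ANCOVA for continuous variables (e.g. collective efficacy scales, income, number of sex trades", with ANCOVA on ranks for non-normal variables such as income. The section states no sidedness, covariate, baseline correlation, ICC, number of groups or group term. It adds a caveat: "we recognize that we may only be able to find trends to report".

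On the unit of randomisation:
- Section 5 (lay summary) says of groups of about 6-10 women that "each group will be randomized to intervention or control conditions".
- Section 6, Phase II: "Women will be part of groups of approximately 10 women each, and each group will be randomized to intervention or control conditions". Sections 10 and 11 also have groups of about 10.
- Section 9, Recruitment and Random Assignment, says both "Eligible and willing participants will be randomized to treatment assignment (ESTIMA or wait-list control group" and, in the next sentence, "The microfinance groups of women (approximately 6-10 per group) will be formed and randomized to intervention or wait-list control condition".
- Section 16, Phase II, assigns women at random as they are recruited and expects to need about 20 to fill one intervention group of 10, which reads as individual assignment.

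On delivery, section 9 lends to women as a group and puts all training in a group format. Under section 15, an unpaid loan leads to dearer or refused later loans for the group.

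**The concern.** Women who train together, borrow together and form a collective are likely to resemble one another on the outcomes that are powered: income, debt, sex trades and collective efficacy. If groups are the randomised unit, the correlation belongs to the design in both arms. If women are assigned individually, it can still arise in the intervention arm through shared delivery. Either way, 48 women carry less information than 48 independent women.

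Two things are at stake. This is the plan's only power statement and it supports n=120, so it shapes how a null result is read. An analysis that ignored the groups would also have standard errors that are too small whenever the within-group correlation is positive. A significant result would then look stronger than it is, in a pilot meant to support funding of a full-scale trial.

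**Working it through.** **Inputs from the documents.** Alpha 0.05; effect 0.5 SD; 60 enrolled per arm and 60 x 0.8 = 48 analysed; group sizes of about 6 to 10.

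**Assumed inputs, because the documents give none.** ICC of 0.02, 0.05 or 0.10 for the adjusted outcome; baseline correlation r of 0, 0.5 or 0.7; equal groups with even retention. The number of groups is bracketed at 60/10 = 6 per arm (48/6 = 8 analysed in each) and 60/6 = 10 per arm (48/10 = 4.8 analysed in each).

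**Step 1: the plan's own figure, independent women.** Non-centrality = 0.5 / sqrt[(2/48)(1 - r^2)], referred to a non-central t with 94 df.
- r = 0: 0.5/0.204 = 2.449. Two-sided power is 67.9%; one-sided is 78.4%.
- r = 0.5: 2.449/sqrt(0.75) = 2.828. Two-sided power is 79.9%.

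So about 80% is reproduced if a one-sided test or r = 0.5 is assumed. Neither is printed.

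**Step 2: allow for groups.** Design effect D = 1 + (m - 1) x ICC, where m is the number analysed per group.
- m = 8: D = 1.14, 1.35, 1.70.
- m = 4.8: D = 1.076, 1.19, 1.38.

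With clustering in the intervention arm only, the variance is multiplied by (1 + D)/2; with both arms clustered, by D. Power for 0.5 SD over ICC 0.10 to 0.02:

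| Reading | 6 groups per arm | 10 groups per arm |
|---|---|---|
| Intervention arm only, 94 df, one-sided, r=0 | 67.3-76.0% | 72.1-77.1% |
| Same, two-sided, r=0 | 55.0-64.9% | 60.4-66.3% |
| Same, two-sided, r=0.5 | 67.3-77.2% | 72.8-78.4% |
| Same, two-sided, r=0.7 | 83.2-90.7% | 87.5-91.5% |
| Same, one-sided, r=0.5 | 78.0-85.8% | 82.4-86.7% |
| Both arms, group-level df (2k - 2, with k groups per arm), two-sided, r=0.5 | 50.0-66.6% | 62.5-73.2% |

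Solving for the r that gives two-sided 80%: 0.53-0.67 with clustering in the intervention arm only (94 df), and 0.60-0.80 with both arms clustered and group-level df. The first range would be somewhat higher with small-sample df.

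**Step 3: detectable effect at two-sided 80% power, ICC 0.02-0.05.** For the intervention-arm-only case a small-sample (Satterthwaite) df is used: (D + 1)^2 / [D^2/(k - 1) + 1/47]. For k = 6 and ICC 0.02 this is 4.580/(1.300/5 + 0.021) = 16.3. The other values are 14.3 (k = 6, ICC 0.05), 28.7 and 26.9 (k = 10). Adjustment multiplies the unadjusted effect by sqrt(1 - r^2).

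| Scenario | r=0 | r=0.5 | r=0.7 |
|---|---|---|---|
| Independent women | 0.58 | 0.50 | 0.41 |
| Intervention arm only, Satterthwaite df | 0.60-0.67 | 0.52-0.58 | 0.43-0.48 |
| Both arms, group-level df | 0.63-0.74 | 0.54-0.64 | 0.45-0.53 |

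**Step 4: false-positive rate if the groups are ignored.** The rate is approximately 2 x [1 - Phi(1.96/sqrt(variance inflation))]. At ICC 0.05:
- Intervention arm only (inflation 1.095 or 1.175): 6.1% or 7.1%.
- Both arms (inflation 1.19 or 1.35): 7.2% or 9.2%.

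Simulation of 200,000 null trials per case gave 6.1% and 7.0%, and 7.2% and 9.3%. At ICC 0.02 in the intervention arm only, the simulated rates are 5.4-5.9%.

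**The case against.** The strongest defence has four parts.

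**The 80% can be right.** The plan names ANCOVA, so a gain from baseline adjustment is plausible, and the hypotheses are directional. This stands. A reader might infer that the figure is a miscalculation, or that 80% is out of reach once groups are counted. The documents support neither. A one-sided test with r = 0.5 still gives 78-87% with clustering in the intervention arm only, and so supports about 80%. A two-sided test at r = 0.7 exceeds 80% in the same setting. The missing sidedness and baseline correlation are omitted detail, not an error.

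**The loss depends on an assumed ICC.** This also stands. At 0.02 in the intervention arm only, it is about two percentage points. The omission itself does not depend on the value chosen.

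**The both-arms figures are severe.** Wait-list women receive the programme only after the 12-month data collection, so no programme-induced correlation exists in the control arm at the analysed time point. Any correlation there would come from how the groups were formed. Those figures are an upper scenario, although group-level df remain relevant if groups are the randomised unit.

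**Silence is not a decision.** The plan lists no model terms at all, so a reader who infers that the analysis will certainly ignore the groups goes too far. What can be said is that no group term is stated, and that standard errors would be too small if none is used and the ICC is positive.

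The pilot caveat limits the consequence. It neither supplies the missing inputs nor corrects a standard error.

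**Conclusion.** The point holds and should be fixed, but it does not undermine the pilot. The power calculation treats women as independent and no group term is stated for the models, while every reading of the plan delivers the programme in groups and most sections randomise groups.

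At an assumed ICC of 0.02-0.10 with clustering in the intervention arm only and individual-level df, the one-sided unadjusted reading gives 67-77% and the two-sided r = 0.5 reading 67-78%. Two-sided 80% needs r of about 0.53-0.67 there, or 0.60-0.80 in the both-arms upper scenario. If groups are ignored and the ICC is 0.05, the false-positive rate of a nominal 5% test is about 6-7%, or 7-9% in the upper scenario.

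These sizes rest on the assumed ICC and r and on 6-10 equal groups per arm. They are normal-theory figures, so they are only approximate for outcomes such as income that will be analysed on ranks.

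**What to change.** Keep n=120 and the caveat that the pilot may show only trends.

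1. Reconcile the unit of randomisation across sections 5, 6, 9 (Recruitment and Random Assignment), 10, 11 and 16.
2. Record a group identifier and add a group term to the section 9 models: a mixed model or a cluster-robust method, with a small-sample correction. Apply it in both arms if groups are randomised, or in the intervention arm only if women are assigned individually.
3. Replace the single 80% with the detectable effect for that analysis over a stated ICC range, giving the sidedness and the assumed baseline correlation. The last two rows of the second table above can serve as the example, with the both-arms row labelled as the upper scenario. Note that the figures are approximate for rank-analysed outcomes.

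Cost: no extra participants or visits. The models become slightly more complex, and the ICC will be estimated imprecisely from 6-10 groups per arm. The printed figure will be less favourable unless a high baseline correlation can be justified (for a two-sided test, about 0.53-0.80 depending on the scenario).
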